Cover Page

Title: Analytic Plan-- Addressing Intersectional Stigma: Testing THRIVE 365 for Black Sexual Minority Men (On The Daily)

NCT Number: NCT05376397

Document Date: 12/18/2023

Analytic Plan

To examine the feasibility and acceptability of iTHRIVE 365, we will evaluate daily self-report engagement data and page access paradata (feasibility) and whether they found it useful, user-friendly, and whether they would recommend it to others (acceptability). To examine the impact of iTHRIVE 365 engagement, we will run a chi-square to test for differences in ART use between days in which participants did and did not engage with iTHRIVE 365. This is better than a day-level approach given there is high ART use in the sample, which limits analytic options given small within- and between-level variance. For psychological outcomes, we will estimate dynamic structural equation models (DSEM) for the intensive longitudinal data (ILD) produced by the daily surveys. DSEM is an analytic approach that combines time-series analysis, multilevel modeling, and structural equation modeling as it can model: within-person lagged associations across many repeated measures, between-person differences in individual-level processes, and multiple latent and outcome variables, respectively. Our models will follow best practices in two-level DSEM for ILD in *Mplus* 8.4, with analyses as multilevel models that specify within-person variance (i.e., change in outcome for a single person from day to day) and between-person variance (i.e., differences between participants' overall outcomes). The standard DSEM approach within *Mplus* uses Bayesian Markov Chain Monte Carlo estimation to aid in convergence and flexibility. For those unfamiliar with Bayesian statistics, there are no *p*-values associated with effects; however, typical frequentist inference can be approximated by calculating a 95% credible interval for each parameter and testing whether 0 is within the interval. Intervals that do not contain 0 are analogous to "significant" in a traditional frequentist analysis.

Specifically, we will examine associations between iTHRIVE 365 engagement and next day outcomes with a multilevel vector autoregressive models (VAR (1)) in the DSEM framework.⁴² All models will adjust the effects of engagement for app availability since app registration occurred starting on day 8 of the study. As an example, the models examining the association between iTHRIVE 365 engagement (T365) and depressive symptoms (Dep) can be written in statistically as

$$\begin{aligned}
 & \text{Within-Person} \\
 & \text{Dep}_{ti} = \alpha_{1i} + \varphi_{1i} \text{Dep}_{(t-1)i}^C + \beta_{1i} \text{T365}_{(t-1)i} + e_{1ti} \\
 & \text{T365}_{ti} = \nu_1 + \varphi_2 \text{T365}_{(t-1)i} + \beta_2 \text{Access}_{ti} \\
 & \text{Between-Person} \\
 & \alpha_{1i} = \gamma_{00} + u_{0i} \\
 & \beta_{1i} = \gamma_{10} + u_{1i} \\
 & \varphi_{1i} = \gamma_{20} + u_{2i}
 \end{aligned} \tag{1}$$

With distributional assumptions,

$$\begin{aligned}
 \mathbf{e}_i & \sim N \left(\mathbf{0}, \text{diag} \left[\sigma_1^2, \sigma_2^2 \right] \right) \\
 \mathbf{u}_i & \sim N \left(\mathbf{0}, \begin{bmatrix} \tau_{00} & & \\ \tau_{21} & \tau_{11} & \\ 0 & 0 & \tau_{22} \end{bmatrix} \right)
 \end{aligned} \tag{2}$$

In the first expression in the within-person equation, Dep is the depressive symptoms outcome, t indexes time (in days, $t = 1, \dots, 14$), i indexes individuals ($i = 1, \dots, N$), α_{1i} is a person-specific intercept for depressive symptoms, φ_{1i} is the autoregressive effect capturing the carryover of depressive symptoms from the previous day to the current day, Dep^C is latent-centered depressive symptoms such that $\text{Dep}_i^C = \text{Dep}_i - \alpha_{1i}$ (latent centering helps alleviate Ludkte's and Nickell's bias in time-series models),⁴³ β_{1i} is a time-varying covariate effect of T365 access the previous day on depressive

symptoms during the current day, and e_i is a normally distributed within-person error with variance σ_1^2 . The second expression in the within-person equation is a probit model because T365 use is dichotomous such that ν_1 is the threshold for T365 use, φ_2 is the carryover effect of T365 use the previous day onto T365 use during the current day, and β_2 accounts for whether person i had access to the intervention at time t .

In the between-person model, γ are fixed effects that capture the average effect of the parameter across all persons, and u are normally distributed random effects capturing person-specific deviations from the fixed effects. The variances of the random effects are captured by the diagonal elements of the tau-matrix; one random effect covariance between depressive symptoms intercepts and the lagged T365 effect is also estimated as denoted by the τ_{10} element in the off-diagonal. Figure 1 features a path diagram for this model.

In line with best practice recommendations for DSEM with small sample sizes,⁴⁴ we will use range restricted priors of $Uniform[0,1]$ for the random effect variances τ_{00} , τ_{11} , and τ_{22} to stabilize the sampling in the MCMC optimization. This approach does not encode subjective prior beliefs but rather just limits the prior's support to range of values that the outcome can take. *Mplus* default priors were used for other parameters that are minimally influenced by sample size including improper $N(0, \infty)$ for regression paths or random effect covariances and improper $InvGamma(-1, 0)$ for within-person error variances. Parameters will be estimated via Markov Chain Monte Carlo with a Gibbs sampler using two chains thinned by 10 iterations with a minimum of 20,000 iterations. Convergence after 20,000 iterations was evaluated using the potential scale

reduction method using a threshold of $\hat{R} \leq 1.10$. We will compute credible intervals with the highest posterior density method.

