Cover Page

Title: Brief Protocol Summary-- Addressing Intersectional Stigma: Testing THRIVE 365 for Black Sexual Minority Men (On The Daily)

NCT Number: NCT05376397

Document Date: 12/18/2023

Brief Protocol Summary

The sample consisted of Black sexual minority men (SMM) living with HIV and connected with the community-based organization, THRIVE SS. THRIVE SS is an Atlanta, GA based CBO that focuses on health equity for Black SMM, most of whom are living with HIV, through cultivating peer support, advocacy, and community building. The study team recruited a nonrandom purposive sample through advertisements on THRIVE SS's social media and email blasts. Eligibility criteria for this analysis were: 16 years old or older, identifying as masculine, identifying as Black/African American, reporting being attracted to and/or sexually active with men, able to complete all procedures in English, mobile access to the internet in order to complete the once-daily survey procedures. After the screening eligible for the study, participants received an invitation to participate in a HIPPA compliant WebEx informed consent meeting and baseline assessment with a trained research assistant. After baseline was a 14-day daily diary study with surveys administered on an Internet-based Qualtrics platform. Across all days, participants received 8 PM text-messages with links to their daily surveys. For those who had not completed the survey by 9:30 PM, they received an automatic reminder message. Surveys included measures of psychological and behavioral variables. We used simple randomization to vary the order of administration of all instruments. In line with a pre-post, one-arm trial, participants did not have access to the iTHRIVE 365 intervention for days 1–7 then received access to register and use the invention for days 8–14. The follow-up assessment occurred at the end of the 2-week daily diary period. We collected summary paradata (i.e., process data detailing app usage) on intervention page access. Participants received \$30 for baseline and follow-up and \$1.50 per survey for the first 7 daily surveys and \$2.50 for the next 7 surveys, with a \$5 bonus for completing all surveys (total maximum: \$93). The Rutgers University institutional review board approved all study procedures.

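### The only planned test of ART use is a chi-square on days that ignores repeated days per participant, so its error rate is not assured

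*SAP*

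**What the plan says.** The Analytic Plan in the SAP gives ART use one test: to "run a chi-square to test for differences in ART use between days in which participants did and did not engage" with the app. The reason offered is "This is better than a day-level approach given there is high ART use in the sample"; the SAP adds that little variance within or between participants narrows the choice of methods. The multilevel method is assigned elsewhere: "For psychological outcomes, we will estimate dynamic structural equation models (DSEM) for the intensive longitudinal data".

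The Brief Protocol Summary sets out the data: "After baseline was a 14-day daily diary study with surveys administered on an Internet-based Qualtrics platform". It adds: "In line with a pre-post, one-arm trial, participants did not have access to the iTHRIVE 365 intervention for days" 1 to 7, with access on days 8 to 14.

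Within its DSEM description the SAP states: "All models will adjust the effects of engagement for app availability since app registration occurred starting on day 8 of the study". The engagement equation there also has a term for the "carryover effect of T365 use the previous day onto T365 use during the current day". The chi-square has no counterpart to either provision. The SAP does not state which days enter the table or what alpha applies.

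**The concern.** There are two separate problems.

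- **Repeated days.** A Pearson chi-square on days assumes that every day is an independent observation, but each participant supplies up to 14. If some men habitually miss doses and some habitually use the app, or if either behaviour runs in streaks, the usual reference distribution is wrong.
- **Days 1 to 7.** Nobody could engage in that week. If those days enter as non-engaged, the contrast partly compares week 1 with week 2, and any change in ART use between the weeks for other reasons looks like an engagement effect.

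The unit is also unclear, because a comparison of days is called better than a day-level approach and no aggregation to participants is described.

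This is the only ART test, and the SAP presents it as evidence on the impact of engagement. The error could run in either direction.

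**Working it through.** **Inputs.** From the documents: up to 14 days per participant, app access on days 8–14 only, and a chi-square by day. Not given: N, alpha for this test, ART rate, engagement rate, ICCs and day-to-day correlation. There is thus no planned figure to reproduce. Everything below rests on assumed values and a two-sided 5% level, with no true engagement effect.

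**Step 1. Clustering by person.** Let ρ_A be the ART ICC, S a participant's number of engaged days, m the days per participant in the table, and σ² the variance of the engaged/not-engaged indicator over those days. With exchangeable days, the true variance of the chi-square's score divided by the variance it assumes is about

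F = 1 − ρ_A + ρ_A × Var(S)/(mσ²), and the real rejection rate is about 2[1 − Φ(1.96/√F)].

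Take engagement probability 0.40 on days 8–14 with ICC ρ_E. Then Var(S) = 7 × 0.40 × 0.60 × (1 + 6ρ_E) = 1.68(1 + 6ρ_E).

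- Days 8–14: mσ² = 7 × 0.24 = 1.68, so F = 1 + 6ρ_Aρ_E.
- All 14 days: mean engagement 0.20, mσ² = 14 × 0.16 = 2.24, so F = 1 − ρ_A + 0.75ρ_A(1 + 6ρ_E).

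| Days | ρ_A | ρ_E | F | Rejection by formula | Simulated, N = 20 / 40 / 80 |
|---|---|---|---|---|---|
| All | 0.6 | 0 | 0.85 | 3.4% | 3.0 / 3.0 / 3.6% |
| All | 0.3 | 0.3 | 1.33 | 8.9% | 8.0 / 8.8 / 7.6% |
| All | 0.6 | 0.6 | 2.47 | 21.2% | 20.6 / 21.0 / 20.2% |
| 8–14 | 0.3 | 0.3 | 1.54 | 11.4% | 11.8 / 11.4 / 11.3% |
| 8–14 | 0.6 | 0.6 | 3.16 | 27.0% | 26.5 / 28.2 / 26.3% |

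(Simulation: ART use 90%, 2,000 replicates per cell.) The test is mildly conservative when only ART use clusters, and liberal when both series cluster. A larger N does not help.

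**Step 2. Adding day-to-day correlation.** A wider null simulation used N = 20, 30, 50; ART use 85, 90, 95%; ART ICC 0.05, 0.10, 0.30, 0.50; three engagement patterns on days 8–14 (person-level probability Beta(0.5, 0.5), Beta(2, 2) or constant 0.5); and 5,000 replicates per cell over 324 cells. Rejection ranges:

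| Lag-1 correlation, both series | Chi-square, all days | Chi-square, days 8–14 | Ordinary Mantel-Haenszel by participant |
|---|---|---|---|
| 0 | 2.5–15.3% | 3.3–22.4% | 2.7–6.0% |
| 0.3 | 6.5–19.4% | 6.0–26.1% | 2.6–7.0% |
| 0.5 | 10.9–24.0% | 9.8–31.0% | 2.9–9.9% |

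Over all 324 cells, a participant-clustered risk difference on days 8–14 (CR2 standard error, N−1 df) rejected 0.2–5.7%. A participant-stratified score with variance taken across participants rejected 0.0–6.0%. With correlation 0.5 in ART use only, the all-days chi-square rejected 4.7–20.0%; in engagement only, 4.6–18.5%. With 20% of surveys missing at random the pattern held: all-days chi-square 3.8–9.6% at correlation 0 and 9.3–17.5% at 0.5, clustered test 0.5–5.4%.

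**Step 3. Days 1–7.** Suppose ART use shifts 5 points between the weeks for reasons unrelated to engagement (assumed; ICC 0.1–0.3). The all-days chi-square then rejects 8.7–31.6% at correlation 0 and 15.2–35.4% at 0.5, against 1.8–5.4% for the clustered test on days 8–14. Under the Step 1 set-up with a 5-point shift (ART use 85% before it, ART ICC 0.3), person-adjusted tests that kept days 1–7 still rejected about 7–29%; with days 8–14 only they rejected about 4–6%. Both repairs are needed.

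**Step 4. Sparse counts.** With N = 20, 95% ART use and mean engagement 0.5 in week 2, there are 20 × 14 = 280 days and 280 × 0.05 = 14 missed-dose days. The engaged share is 0.5 × 7/14 = 0.25, so 14 × 0.25 = 3.5 missed doses are expected on engaged days. In simulation the smallest expected count was below 5 in 74–89% of such tables.

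**The case against.** The strongest reply is that large inflation needs assumptions the documents do not supply. With no lag-1 correlation, a re-run of the Step 2 grid gave a median all-days rejection of 5.7%, with 86 of 108 cells at or below 7.5%. Every cell above 10% combined strongly U-shaped engagement with ART ICC of at least 0.3; at ICC 0.05–0.10 the range was 4.1–7.4%. The carryover term is a parameter to be estimated, not a belief that carryover exists, and it concerns engagement rather than ART use. All of this stands, and it rules out a claim that the test is certainly inflated. It does not supply the missing provision: the SAP calls the variances small but gives no values, and a ratio of two small variances can still be large.

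The SAP's wording may mean that aggregation was intended. That is possible but not stated, so clarification should come first. The days 1–7 problem is also conditional: it arises only if those days enter and ART use shifts between the weeks.

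High ART use does limit the options, and the low power reported below bears that out. It can justify a simpler method, but it does not make one man's days independent.

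Finally, this is a one-arm pilot with self-selected engagement, and no alpha, power, decision rule or primary outcome rests on the test. That limits the consequence, but the p-value would still be uninterpretable.

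**Conclusion.** The concern holds. As written, the only ART test makes no allowance for up to 14 days per participant and none for the access-free week. Confidence is high on that omission. The size and direction of the error cannot be fixed from the documents. Under the assumed ranges, a nominal 5% all-days test rejects anywhere from 2.5% to 24.0% of the time with no shift in ART use between weeks, and up to 35.4% with an assumed 5-point shift. It is near nominal or mildly conservative when engagement varies only within person and days are not serially correlated. It is well above nominal when both series cluster by person or run in streaks. The practical consequence is a misleading exploratory p-value. It should be fixed, but it does not threaten a decision built into the trial.

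**What to change.** 1. Ask the sponsor what the day-level remark means. Then state the unit of analysis, which days enter, and how repeated days are handled.
2. Restrict the engagement contrast to days 8–14. Stratifying by app availability gives the same contrast, since days 1–7 hold no engaged days.
3. Replace the chi-square with one named main analysis, for example a participant-clustered risk difference with 95% CI, using a small-sample-corrected robust standard error (such as CR2) and N−1 df. Other methods that respect the clustering would also serve.
4. As a within-person sensitivity analysis, use a participant-stratified Mantel-Haenszel score with variance taken across participants; the ordinary variance assumes no day-to-day correlation within person. State that the main analysis also contains between-person differences, so the two can differ.
5. Report how many participants vary in both ART use and engagement. If missed doses are too few to test, report counts only.
6. Describe the result as an exploratory association in self-selected users. The Protocol is in the past tense and the SAP already describes ART use in the sample, so label the change post hoc if the data had been seen.

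The cost is SAP wording and a few lines of code on data already planned. Days 1–7 stop informing this contrast. The clustered test is very conservative when missed doses are few and concentrated: it rejects 0.2–0.7% at N = 20, 95% ART use and ICC 0.5, where the median number of informative participants is 1–2. Power is low. If missed doses are halved on engaged days (assumed; ART use 90–95%, ICC 0.1–0.5, correlation 0 or 0.5), it is 0.3–16% at N = 20, 1–23% at N = 30 and 4–41% at N = 50, with medians of 4%, 8% and 15%. A non-significant result must not be read as no association.

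### The SAP says engagement effects are adjusted for app availability, but equation (1) puts Access only in the model for app use, not in the outcome equation that holds beta_1

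*SAP*

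**What the plan says.** For the psychological outcomes the SAP sets this target: "we will examine associations between iTHRIVE 365 engagement and next day outcomes". It then promises: "All models will adjust the effects of engagement for app availability since app registration occurred starting on day 8 of the study". Equation (1), with depressive symptoms as the worked example, has two within-person parts:

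- **Outcome:** Dep on day t depends on a person intercept alpha_1i, the previous day's centred Dep (phi_1i), the previous day's T365 (beta_1i) and an error.
- **App use:** a probit for T365 on day t, with threshold nu_1, the previous day's T365 (phi_2) and Access_ti (beta_2). Of beta_2 the SAP says that it "accounts for whether person i had access to the intervention at time t".

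The between-person equations for alpha_1i, beta_1i and phi_1i contain no covariate. Equation (2) makes the residual matrix diagonal. On the random effects, the text says "one random effect covariance between depressive symptoms intercepts and the lagged T365 effect is also estimated"; both of these belong to the Dep equation.

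The Protocol (Brief Protocol Summary) describes the design with the words "In line with a pre-post, one-arm trial". Participants had no access on days 1-7, then "received access to register and use the invention for days" 8-14. Payment was $1.50 "per survey for the first 7 daily surveys and" $2.50 for the next seven.

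**The concern.** The promised adjustment concerns the effects of engagement. For the psychological outcomes that effect is beta_1, and the equation that estimates it contains nothing about availability. T365 is zero by design on days 1-7, so beta_1 is in part a comparison of the second week with the first. The two weeks differ in access, in payment per survey and in time since enrolment. If the outcome shifts for any reason other than use, part of the shift is credited to use. The SAP treats a 95% credible interval that excludes 0 as the analogue of significance. A week-to-week change could therefore be reported as an engagement effect, to a reader who has been told that availability was adjusted for.

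Two gaps in wording add to this. The SAP says that beta_1i "is a time-varying covariate effect of T365 access the previous day on depressive" symptoms the next day, although T365 means use elsewhere, so use and availability are not kept apart. Nor does it say whether Access_ti is 1 on days 8-14 for everyone or only once a person has registered.

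**Working it through.** The documents give no figure to reproduce on this point. They also give no N, use rate or size of phase change, so all such inputs below are assumptions.

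**1. Structure.** Access occurs once in equation (1), in the probit. Dep does not appear in the probit, the residuals are uncorrelated, and no random effect is shared. With T365_(t-1) observed and entered as 0/1, the likelihood splits into a Dep factor and a T365 factor. Access sits in the second and cannot move beta_1, which sits in the first. With missing T365 days, or if the software lags the latent probit response, the split is not exact, but there is still no path from Access to Dep.

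**2. How far beta_1 compares weeks.** Each person has 13 lagged rows (outcome days 2-14). On outcome days 2-8 the previous day had no access, so 7 of the 13 rows can only be non-use. With use rate p on access days there are 13 - 6p non-use rows on average. The forced share is 7/(13 - 6p): 7/11.2 = 63% at p = 30% and 7/10 = 70% at p = 50%.

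**3. Share of a phase change absorbed, ignoring autoregression.** Let the outcome change by delta from day 8.

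- Cov(T365_(t-1), Access_t) = (6p/13)(1 - 7/13) = (6p/13)(6/13)
- Var(T365_(t-1)) = (6p/13)(1 - 6p/13)
- Absorbed share = (6/13)/(1 - 6p/13)

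| p | share absorbed | beta_1 if delta = -0.2 |
|---|---|---|
| 30% | 0.462/0.862 = 54% | -0.11 |
| 40% | 0.462/0.815 = 57% | -0.11 |
| 50% | 0.462/0.769 = 60% | -0.12 |

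If the change starts one day later, with lagged access, the numerator is 7/13 and the shares at 30% and 50% are 62.5% and 70%.

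**4. Simulation of the Dep equation.** This was a Gibbs sampler with latent centring, random intercept, slope and autoregression, an estimated intercept-slope covariance, the SAP's Uniform[0,1] priors on the three variances, and 95% highest-density intervals. Assumed: residual SD 1, intercept SD 0.7, mean autoregression 0 or 0.3 (SD 0.1), use-threshold SD 0 or 1, p 30-50%. There were 200 replicates per cell, each with one chain of 1,300 iterations. True beta_1 = 0 unless stated.

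| Setting | mean beta_1 | interval excludes 0 |
|---|---|---|
| N = 50, term -0.2 SD from day 8, as planned | -0.10 to -0.14 | 10-21% |
| same, Access_t in Dep equation | -0.02 to 0.01 | 3-7% |
| same, Access_(t-1) in Dep equation | -0.02 to 0.01 | 2-5% |
| term 0, as planned | 0.00 | 2% |
| term -0.1, as planned | about -0.07 | 5-10% |
| term -0.4, as planned | -0.21 to -0.26 | 31-60% |
| N = 30, term -0.2, as planned | not tabulated | 6-10% |
| N = 100, term -0.2, as planned | not tabulated | 29-41% |

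A linear drift of -0.2 over the 14 days gives -0.05 as planned and -0.01 with Access_t. If 40% never register, beta_1 is -0.11 as planned, -0.01 with Access coded as days 8-14, and 0.00 with Access coded as registered.

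**5. Does Access in the probit help?** Dep equation and probit were fitted jointly (N = 50, p = 40%, 80 replicates, assumed N(0,25) priors in the probit). With no missing days beta_1 is -0.10 with or without Access in the probit. With 20% of days missing it is -0.12 with Access in the probit, -0.11 without, and 0.02 with Access in the Dep equation. The Monte Carlo SE of these means is 0.011-0.017.

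**6. Cross-check by within-person least squares.** With N = 30 or 60, p = 0.3, 0.5 or 0.8, autoregression 0.3 and a shift of -0.3 SD, beta_1 is -0.13 to -0.18. Adding current and lagged Access keeps it between -0.014 and 0.019 across all 18 scenarios, with false positives of 3.7-8.3%.

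**7. Secondary: phi_2.** The threshold nu_1 has no person-specific term, so stable differences between users enter phi_2. With no true carryover, a pooled probit on days 8-14 gives phi_2 of about 0.3, 0.8 and 1.2 for assumed threshold SDs of 0.5, 1 and 1.5. This does not affect beta_1.

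**The case against.** The strongest reply is that the harm is hypothetical. No document says that the outcome changes between the weeks for reasons other than use, and nothing links the survey payment to depressive symptoms. That stands, and it is why the size is stated conditionally.

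A second reply is that adjusting might mean only modelling use given access, which the probit does. But the object of the sentence is the effects of engagement, and the probit does not touch those. Equation (1) is offered as an example, and Figure 1 is not in the text available. The SAP calls it a path diagram of this model, so a figure with an Access-to-Dep path would itself have to be reconciled with the equation.

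Third, adding Access changes the estimand: it largely removes the comparison of weeks and leaves self-selected use against non-use on days 8-14. That also stands; its price is given with the fix.

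Fourth, the simulations are approximate. They are not Mplus runs, use far fewer iterations than the planned 20,000, and depart from the SAP's improper priors in the probit. The latent-lag reading was not simulated. With 200 replicates the Monte Carlo SE of an exclusion rate is about 1.7 points at 6% and 2.1 at 10%, so the lowest rates cannot be told apart from 5%. The figures show direction and rough size. The mismatch itself does not depend on them.

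**Conclusion.** The plan is wrong as written: it claims an adjustment that its stated model does not make. This follows from equations (1) and (2) and the description of the random effects, without any assumed input. The effect on the results is conditional. With no phase change the bias is nil. Given one, somewhat more than half passes into beta_1 in the simple case with use rates of 30-50%, less under gradual drift, and the chance of an interval that wrongly excludes 0 rises with N and with the size of the change. The point should be corrected before the psychological results are interpreted.

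**What to change.** Add Access (availability or phase) to the Dep equation and to the equation of every other psychological outcome. State whether it is coded as days 8-14 for all or as registered, and whether it enters at t or t-1. Report beta_1 with and without it, described as the next-day association given availability. If the sponsor prefers to keep equation (1), the statement that engagement effects are adjusted for app availability should be withdrawn. If use is meant, replace access by use in the description of beta_1i. Check Figure 1 against the final equation. Separately, say that phi_2 will not be read as within-person carryover, or give the threshold a random effect.

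The cost is Mplus syntax and SAP wording, with no new data. In the N = 50 simulations the posterior SD of beta_1 rises 4-13% with Access_t and 6-20% with Access_(t-1). Access can also absorb benefit that lasts beyond the next day. With an assumed lasting effect of -0.2 after first use and no phase change, beta_1 goes from -0.14 to -0.11 (Access_t) or -0.10 (Access_(t-1)). A pure next-day effect of -0.2 is not absorbed: the estimate is -0.18 either way. The SAP should state this choice of estimand.

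### The engagement line of equation (1) gives every man the same threshold, so if men differ in usual use φ₂ mixes those stable differences with day-to-day carryover

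*SAP*

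**What the plan says.** All of this is in the SAP, Analytic Plan.

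- **Engagement line of equation (1).** Use on day t depends on ν₁, on φ₂ times use on day t−1, and on β₂ times Access. None of the three coefficients has a person index. The text below equation (2) says that ν₁ "is the threshold for T365 use" and that φ₂ "is the carryover effect of T365 use the previous day onto T365 use during the current day".
- **Symptom (Dep) line.** Here α₁ᵢ "is a person-specific intercept for depressive symptoms", lagged symptoms are centred on it, and the plan notes that "latent centering helps alleviate" two known biases. Lagged use is printed without centring; its coefficient β₁ᵢ "is a time-varying covariate effect of T365 access the previous day on depressive" symptoms.
- **Between-person part.** There are equations for α₁ᵢ, β₁ᵢ and φ₁ᵢ only. Range-restricted priors are given "for the random effect variances" τ₀₀, τ₁₁ and τ₂₂, and "one random effect covariance between depressive symptoms intercepts and the lagged T365 effect is also estimated". Nothing describes a man's usual level of use or links it to α₁ᵢ.
- **Inference rule.** A 95% credible interval is calculated for each parameter, and one that excludes 0 is read as the counterpart of a significant result.

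The Protocol (Brief Protocol Summary) states that the app was unavailable on days 1–7 and available on days 8–14.

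**The concern.** Among the reasons for choosing DSEM, the SAP lists that it can model "between-person differences in individual-level processes". The symptom line does so; the engagement line does not. When men differ in usual use, use yesterday marks a frequent user. With one shared threshold, φ₂ is the only term that can express this. It then measures a mixture of habit within a man and differences between men, although the plan labels it as the first alone. Under the plan's own interval rule, an app with no carryover could be reported as having it, and a larger sample would make that report more certain.

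There is a second, narrower question. Lagged use enters the symptom line uncentred, and usual use has no link to α₁ᵢ. Part of any between-person relation between using the app and being less (or more) symptomatic could therefore enter γ₁₀, the average engagement effect.

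**Working it through.** **Inputs.** The plan states no figure for φ₂, so there is none to reproduce. From the documents: the form of equation (1), and access on days 8–14 only, so lagged use is 0 for everyone on day 8. Assumed, because the documents are silent: sample size, mean use and how far men differ. Taking Access as calendar availability, days 1–7 contain no use and say nothing about φ₂.

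**Closed form, true carryover 0.** Let man i use the app with probability pᵢ on each day from 8 to 14.

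- P(use | use the day before) = E[p²]/E[p].
- P(use | no use the day before), days 9–14 = (E[p] − E[p²])/(1 − E[p]).
- At mean use 0.5, each man gives one lag-0 day on day 8 (use probability 0.5) and on average 6 × 0.5 = 3 on days 9–14. The pooled value is (0.5 + 3 × the second probability)/4.
- φ₂ = Φ⁻¹(first) − Φ⁻¹(pooled).

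| Usual use | Var(p) | After use | After no use, days 9–14 | Pooled with day 8 | φ₂ |
|---|---|---|---|---|---|
| Identical men | 0 | 0.50 | 0.50 | 0.50 | 0 |
| Beta(8,8) | 0.0147 | 0.529 | 0.471 | 0.478 | 0.074 + 0.055 = 0.13 |
| Beta(2,2) | 0.05 | 0.60 | 0.40 | 0.425 | 0.253 + 0.189 = 0.44 |
| Beta(.5,.5) | 0.125 | 0.75 | 0.25 | 0.3125 | 0.674 + 0.489 = 1.16 |

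**How often the interval excludes 0.** Simulation of the printed engagement line, true carryover 0, mean use 50%, 4,000 replicates, Wald intervals standing in for credible intervals:

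| Usual use | N = 30 | N = 75 |
|---|---|---|
| Identical men | 4.6% | 5.0% |
| Beta(8,8) | 11.5% | 21.5% |
| Beta(2,2) | 63% | 96% |
| Beta(.5,.5) | 99.9% | 100% |

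**A different form of heterogeneity.** With normally distributed thresholds of SD ω and mean use of 20–50%, a true φ₂ of 0 reads as 0.29–0.34 (ω = 0.5), 0.75–0.86 (ω = 1) and 1.13–1.29 (ω = 1.5). A true φ₂ of 0.5 reads as 0.76–0.81, 1.16–1.31 and 1.50–1.69. At ω = 0 the estimate is correct in both cases.

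**With a random threshold.** In a Gibbs-sampler fit (N = 1,000, 8 replicates, ω = 1, true φ₂ = 0), the printed model gave 0.82. A model with a person-specific threshold, allowed to covary with α₁ᵢ and β₁ᵢ, gave −0.005. In small samples the repair is imperfect. Penalised maximum likelihood at N = 30 or 75 gave:

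- −0.057 to +0.029 when men differ and mean use is 50%;
- −0.07 (N = 75) or −0.10 (N = 30) when men do not differ;
- −0.12 at 11% use (N = 30, threshold SD 0.7);
- −0.09 (N = 30) or −0.11 (N = 75) when use falls by 0.1 probit per day.

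**γ₁₀, true effect 0, printed model.** With a stable tendency to use the app correlated −0.3 to −0.7 with usual symptoms, the bias was −0.006 to −0.077 innovation SDs. The interval excluded 0 in 4.4–8.8% (N = 30) and 3.2–15.8% (N = 75). The Gibbs fits, scaled so that τ₀₀ + σ₁² = 1, gave 0.019 at correlation 0.3, 0.019 to 0.054 at 0.5 (depending on the variance split), −0.040 at −0.5, and −0.003 (Monte Carlo SE 0.008) at 0. If use only responds to symptoms already experienced, the bias was at most 0.007 in size.

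**The case against.** The strongest reply is that φ₂ is not what the trial is about. The stated target is the association of engagement with next-day outcomes, which is γ₁₀, and feasibility rests on self-reported engagement and page-access data. No objective depends on φ₂. This stands, and it lowers the priority. It does not remove the point, because the plan gives φ₂ a substantive meaning and an inference rule that covers each parameter.

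A second reply is that Access is indexed by person. If it means personal registration, it absorbs men who never registered. That also stands, but it leaves differences among registered men untouched.

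Third, the size is entirely assumed. It is; hence the range, which starts at 0.

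Fourth, Figure 1 could show a person-specific threshold. It is not reproduced in the text I have, but the equation, its explanation and the list of variances all agree that there is none.

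A reader might go further and infer that the inflated φ₂ contaminates the main engagement effect. The documents do not support that: the two lines share no parameter, so with complete use data the bias stays in φ₂. The opposite inference, that γ₁₀ is safe in all circumstances, is also too strong. The plan specifies joint Bayesian estimation and does not say how missing use is handled, and the Protocol's reminders and completion bonus show that missed diaries were foreseen. If missing use is imputed inside the model, the engagement line helps to fill in the lagged use in the symptom line, and the separation is no longer guaranteed.

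**Conclusion.** The point holds for φ₂. As printed, it does not estimate carryover within a man unless men with access share the same usual use. With no true carryover it reads as about 0.1 to 1.3 on the probit scale under the heterogeneity assumed here, and as about 0 without heterogeneity. How far these men differ cannot be read from the documents.

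For γ₁₀ the point is much weaker: a between-person part of roughly 0.01 to 0.08 SD, and only if a stable tendency to use the app is related to usual symptoms. It would be wrong to infer that the planned engagement effect is invalid. Equation (1) can remain the primary model for it. Whether Access belongs in the symptom line is a separate matter and is not judged here.

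The small-sample results for the random threshold rest on maximum likelihood with a weak penalty, complete diaries and days 8–14 only, not on the planned Mplus fit. Priority: minor to moderate.

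**What to change.** 1. Replace ν₁ with ν₁ᵢ = γ₃₀ + u₃ᵢ, keep Access, estimate the variance of u₃ᵢ, and report φ₂ from this model. State a weakly informative prior whose upper limit is well above 1: a threshold SD of 1.5 already means a variance of 1.5² = 2.25, which the Uniform[0,1] used for the other random effects would exclude. If this is not done, do not describe or test φ₂ as carryover.

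2. Keep equation (1) as primary for γ₁₀. As an optional sensitivity analysis, let u₃ᵢ covary with u₀ᵢ, and say that no single specification is unbiased under every mechanism. A version that also put same-day and previous-day symptoms in the engagement line was off by about +0.03 to +0.04 when use responded to a longer run of past symptoms. I have not checked the covariance-only version under such feedback.

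3. State whether T365 is centred in the symptom line, and whether Access means calendar availability or personal registration. The text also calls lagged T365 access in one place and use in others. Say how missing T365 values are handled.

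**Cost.** SAP wording and one variance per model, with data already planned. The standard error of φ₂ rises by about 7–8% if men do not differ and by up to 56–57% under Beta(.5,.5). Expect some negative bias in φ₂, about −0.05 to −0.13, if men hardly differ, use is rare or use declines over the days, and more at very low use with a small sample. With complete use data and the covariances of u₃ᵢ with the other random effects set to 0, γ₁₀ and its standard error are unchanged by item 1.
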